## STUDY PROTOCOL

### 1. BACKGROUND AND RATIONALE

#### 1.1. General Introduction

The concept of immediate implant was proposed about forty years ago (Schulte and Heimke 1976; Schulte et al. 1978). Over the past few decades, several clinical trials had demonstrated immediate implantation has high survival rate and stable interproximal bone levels (Becker et al. 1998; Chen et al. 2007; Lazzara 1989; Sanz et al. 2014; Schropp et al. 2003), similar to conventional delayed implant placement. Compared to delayed placement, immediate implantation is able to reduce the number of clinical visits and surgical procedures, by this diminishing patient morbidity, and in some cases, enabling immediate restoration (Lang et al. 2012). In addition to these advantages, it has been suggested that immediate implant preserves alveolar bone dimensions (Denissen et al. 1993; Lazzara 1989; Paolantonio et al. 2001; Watzek et al. 1995). However, several experimental studies and clinical trials demonstrated significant changes of bony ridge dimensions in the surgical site of immediate implantation (Botticelli et al. 2004; Botticelli et al. 2006).

Generally, the dimensional change of buccal site is greater than that of the lingual/palatal site (Botticelli et al. 2004; Brownfield and Weltman 2012; Lee et al. 2014). The buccal bone (Lee et al. 2014) or buccal ridge dimensional alteration (Grunder 2011; van Kesteren et al. 2010) following immediate implant placement without placing any bone graft or tissue graft is about 1 to 1.5 mm within one year follow-up. The change of bone/ridge dimension also accompanies with gingival recession. The mean mid-buccal gingival recession is approximately 0.5 to 1mm within one year follow-up following immediate implantation and advanced mid-buccal gingival recession (>1 mm) sometimes happens (Cosyn et al. 2012). Many clinicians try to prevent the changes of soft tissue and hard tissue in the esthetic demanding sites by using different methods. The effect of placing bone grafts and/or immediate temporization has been proved on compensating soft tissue and hard tissue collapse (Cosyn et al. 2012; Tarnow et al. 2014). However, the use of autogenous tissue graft or alternative graft, such as collagen matrix and acellular dermal matrix, combined with immediate implant is equivocal.

Some experimental studies (Berglundh and Lindhe 1996) and clinical studies (Linkevicius et al. 2009; Linkevicius et al. 2014; Vervaeke et al. 2014) showed tissue thickness is negatively associated with the resorption of alveolar bone following implant placement. Therefore, augmenting soft tissue by tissue graft or acellular dermal matrix in the immediate implantation site may prevent the resorption of bone. The limited change of alveolar bone level also prevents gingival recession. Additionally, soft tissue augmentation combined with immediate implantation can directly compensate the dimensional alteration of ridge following extraction (Grunder 2011) and also increases width of keratinized gingiva by two-stage approach (Covani et al. 2007; Jyothi et al. 2013).

Autogenous soft tissue graft has been utilized in ridge augmentation (Allen et al. 1985; Studer et al. 2000), root coverage (Cairo et al. 2014; Langer and Langer 1985), extension of keratinized gingival width (Cairo et al. 2014), gingival thickness augmentation (Muller et al. 1998), and as a barrier in wound healing (Ellegaard et al.

1974; Nelson 2001). Subepithelial connective tissue graft (SCTG) or free gingival graft (FGG) is usually harvested from palate (Langer and Langer 1985; Sullivan and Atkins 1968) given palate provides a large area of keratinized tissue. A number of studies have demonstrated clinical superiority of autogenous soft tissue grafts compared to the available substitutes used in procedures of root coverage (Chambrone et al. 2010; Oates et al. 2003) and keratinized gingiva augmentation(Thoma et al. 2009).

In implant therapy, soft tissue grafts are utilized in ridge reconstruction (Grunder 2000), coverage of crown margins or implant surface (Burkhardt et al. 2008; Lee et al. 2015a), and keratinized tissue extension (Stimmelmayr et al. 2011; Yan et al. 2006). Soft tissue grafts have also been employed to seal extraction socket following immediate implant placement and at the same time to increase the width of keratinized gingiva (Edel 1995; Evian and Cutler 1994; Landsberg and Bichacho 1994; Rosenquist 1997). Combination therapy of soft tissue and osseous grafting with or without a barrier in conjunction with immediate implantation has been proposed by several clinicians to address vertical and horizontal ridge dimensional reduction (Grunder 2011), gingival recession(Migliorati et al. 2015; Yoshino et al. 2014) and to increase width of keratinized gingiva (Covani et al. 2007; Jyothi et al. 2013). These procedures primarily aim to improve the esthetic outcomes following immediate implant placement.

A range of biomaterials, including acellular dermal matrix and xenogeneic collagen matrix, have been developed to replace autogenous soft tissue grafts and to reduce patient morbidity. AlloDerm® Regenerative Tissue Matrix (RTM) is one of the most widely used alternative tissue grafts in dentistry. It is an acellular dermal matrix (ADM) that is derived from donated human skin and is minimally processed to remove epidermal and dermal cells with nondenaturing detergent while preserving the extracellular matrix. The removal of viable cells and antigens during the decellularization process minimizes the risk of rejection and inflammation at the surgical site. Then, a cyropreservant is added to avoid crystal formation, and then resulting tissue matrix is freeze-dried. The remaining matrix serves as a framework for cellular infiltration and vascularization. ADM is indicated for soft tissue augmentation (Batista et al. 2001; Griffin et al. 2004; Park and Wang 2006), gingival recession defect coverage (Andrade et al. 2008; Tal et al. 2002), keratinized gingiva extension (Harris 2001; Yan et al. 2006), and extraction socket coverage (Fowler et al. 2000; Froum et al. 2004; Park 2011) for both teeth and implants. Basically, ADM can be used in all the procedures that the soft tissue graft is indicated for.

Although the application of soft tissue augmentation combined with immediate implant has been reported in some studies, there are only few studies directly comparing the esthetic outcomes of immediate implant combined with soft tissue augmentation to immediate implant alone (Lee et al. 2015b). The evidence regarding the clinical effects of placing acellular dermal matrix at the site of immediate implant is less. It is necessary to conduct a clinical trial evaluating the impact of immediate implant combined with or without soft tissue augmentation on preserving tissue contour.

## 1.2. Rationale and justification for the Study

**a. Rationale for the Study Purpose**

The results of a current systematic review indicated immediate implant combined with autogenous tissue graft is able to maintain the level of gingiva, increase gingival thickness and extend the width of keratinized gingiva (Lee et al. 2015b). However, there is lack of clinical trials directly comparing the esthetics-related clinical outcomes of immediate implant combined with or without soft tissue augmentation.

The purpose of the randomized controlled trial is to evaluate the esthetic outcomes following immediate implant combined with the autogenous tissue graft or acellular dermal matrix compared to immediate implant alone. Changes of ridge dimension, gingival level, gingival thickness, width of keratinized tissue and bony structure will be assessed. SCTG is utilized instead of FGG because SCTG has less morbidity of the donor site and better esthetic outcomes than FGG (Del Pizzo et al. 2002). ADM is utilized because it is the one of the most widely chosen substitutes for autogenous tissue graft in all kinds of procedure and has many published clinical results (Gapski et al. 2005).

**b. Rationale for Materials Selected**

SCTG will be harvested from the palate and the required size depends on the size of the surgical site. Generally, the width of the tissue graft should be sufficient to cover the adjacent interproximal papillae, and the length could be standardized as 10 mm. The size of the tissue graft is able to cover the area usually having the most significant dimensional changes following extraction (Morimoto et al. 2015; Tarnow et al. 2014). The thickness of harvested tissue graft will be trimmed to the range from 1-1.5 mm (Hurzeler and Weng 1999).

The ADM is a commercial product and has multiple sizes available. One piece of 10mmx10mm ADM can be trimmed to an appropriate size defined by the criteria for SCTG. According to the manual instruction, the thickness of ADM ranges from 0.9-1.6mm which will be close to the thickness of SCTG utilized in this study.

**c. Rationale for Study Population**

The study will recruit subjects who have single unrestorable tooth planned for an implant placement. The tooth should have acceptable periodontal condition and locates in the oral esthetic zone, maxillary premolars to premolars. The surgical sites should have intact bony wall, but minor dehiscence or fenestration, up to 3mm, is allowed. These criteria justify the evaluation of esthetic outcomes in the site of immediate implantation.

**d. Rationale for Study Design**

The randomized controlled trial (RCT) is usually considered the gold standard for a clinical trial and it is able to provide the highest level of evidence within all the study designs (Howick et al. 2011). RCT can be used to test the efficacy or effectiveness of various types of medical/dental intervention. It is the most appropriate study design for the aim of the study.

## **2. HYPOTHESIS AND OBJECTIVES**

### **2.1. Hypothesis**

The hypothesis is that ridge dimensional reductions in the sites of immediate implant combined with autogenous tissue graft/acelluar dermal matrix are significantly less than the sites of immediate implant alone. Soft tissue augmentation is able to increase gingival thickness and limit resorption of bone by expanding the dimension of peri-implant mucosa. In addition to limited changes of ridge dimension and increased gingival thickness, stable gingival level and increased width of keratinized gingiva could also be found following soft tissue augmentation.

Placement of acellular dermal matrix has comparable clinical outcomes to placement of autogenous tissue graft because the clinical trials of mucogingival surgery, such as root coverage, show acellular dermal matrix is as effective as autogenous tissue graft.

### **2.2. Primary Objectives**

This randomized controlled trial aims to evaluate the esthetic outcomes following immediate implant combined with the autogenous tissue graft or acellular dermal matrix compared to immediate implant alone. Changes of ridge dimension, gingival level, gingival thickness, and width of keratinized tissue will be assessed.

### **2.3. Secondary Objectives**

In addition to the esthetics-related clinical outcomes, the change of bony structure will also be measured. The alteration of bony structure around an implant is an important clinical parameter indicating the long term stability of the implant. The radiographic change of alveolar bone level will be measured on the images of periapical radiograph. The change of bone dimension will be measured on the images of cone beam computed tomography (CT)

### **2.4. Potential Risks and Benefits:**

#### **a. End Points - Efficacy**

All eligible patients have an unrestorable tooth planned for single implant placement. Therefore, all patients in different groups will at least receive the appropriate treatments. The patients will not have additional clinical benefits by participating in this clinical study, but the patients will have discounted treatments (extraction, implant placement, soft tissue augmentation, radiographic examination).

#### **b. End Points - Safety**

##### **1) Study related risks:**

Initial infection, pain or esthetically adverse outcome related to implant placement; inability to stabilize the implant due to poor quality of bone; implant failure and need for removal; discomfort in function and/or lack of satisfaction with the restoration for other reasons. If the implant has to be removed due to severe symptoms and unacceptable clinical outcomes, the patient will be immediately excluded from the

study and receive appropriate treatments. The patients will have the same risks if they receive the same treatment without participating in the study.

2) Protection against risks:

All efforts will be made to minimize risks to all and every participant: only sites with healthy or almost healthy bone levels will qualify for the study to avert esthetic concerns, restorative and functional expectations will be discussed and explained.

### **3. STUDY POPULATION**

#### **3.1. List the number of subjects to be enrolled.**

**The primary outcome is ridge dimensional alteration at six months after surgery while the secondary outcomes are changes of gingival level, gingival thickness, width of keratinized gingiva, alveolar bone level and bone dimension.** Based on the preliminary results, 11 subjects per group need to be recruited to have 80% power to detect a 1 mm difference with 0.85 mm standard deviation in ridge dimensional change between groups. We plan to enroll 14 subjects in each group to account for potential dropout. The subjects will be recruited from the patients enrolled in the clinics of University of Texas Health Science Center at Houston School of Dentistry (UTSD) and Periodontal and Implant Surgeons of Houston (PISH). There will be no restriction on gender or race.

#### **3.2. Criteria for Recruitment**

The study aims to recruit patients enrolled in the clinics of UTSD and PISH. Therefore, all the patients will have basic dental examinations following the UTSD policy and PISH policy. The clinicians and dental students will be told the information of the study and they will be able to preliminarily screen the potential subjects based on the selection criteria. If the patients are potentially eligible and interested in participating the study, patients will be screened by one of the investigators ([name], [name], [name]); only these investigators will be obtaining the informed consent form. If additional investigators will be included in the study, we will apply for an IRB modification prior to their participation in the study. The qualified subjects will be asked to sign the informed consent form and attend the necessary appointments of the study.

#### **3.3. Inclusion Criteria**

Forty two subjects will be recruited among the patients attending the Clinic for Graduate Periodontics, UTSD, and the Clinic of PISH, who are in need of a tooth extraction at the maxillary premolar, canine and incisor region, and subsequent single implant placement. The reasons for extraction will include poor endodontic prognosis and/or unrestorable teeth (extensive caries, traumatic fractures, fractures of endodontically treated teeth, root perforation, root resorption with or without radiographic periapical lesion up to 3 mm in diameter). All subjects are  $\geq 18$  year-old and systemically healthy or with controlled common systemic conditions (controlled hypertension, controlled diabetes HbA1c up to 7 %). The adjacent teeth have to be present and the eligible tooth has esthetically acceptable buccal gingival margin position prior to surgery, compared to neighboring teeth and contralateral tooth, and adequate width of buccal keratinized gingiva( $\geq 3$ mm). The level of radiographic bone

level has the distance from CEJ to interproximal crest up to 4 mm.

Location of buccal alveolar crest has to be generally within 4 mm from the free gingival margin, verified after the extraction, before randomization; and fenestration, if present, up to 3mm in diameter at the apical part of the root and affecting less than 30% of the buccal socket wall.

### **3.4. Exclusion Criteria**

Patients will be excluded if they currently smoke exceeding 10 cigarettes/ day, have severe parafunctional habits, malocclusion or intent of orthodontic therapy in the future and are pregnant. The teeth in the surgical site will be excluded if there is advanced periodontal disease or periapical lesion causing significant bony defects that are beyond the criteria mentioned at Section 3.3. The patient who is allergy to antibiotics contained in the ADM (Gentamicin, Cefoxitin, Lincomycin, polymixin B and Vancomycin) will not be included in the immediate implant combined with ADM group.

### **3.5. Withdrawal Criteria**

A subject may be discontinued from participation in the study for any of the following reasons:

1. Withdrawal of consent
2. Subject noncompliance with the protocol, as determined by the investigator
3. Any event or condition that would make continued participation in the study not in the best interest of the subject, as determined by the investigator
4. Pregnancy
5. Development of any medical condition that might affect the treatment and clinical outcomes, as determined by the investigator.
6. Initiation of any treatment or exposure that might affect the outcomes of implant therapy, as determined by the investigator.
7. Investigator discretion

### **3.6. Subject Replacement**

Subjects who withdraw from the study can be replaced. However, to complete the study within the time allocated, centers will not enroll subjects after 24 months from enrollment initiation.

## **4. TRIAL SCHEDULE**

There will be eight appointments including the baseline appointment and seven follow-up appointments (2, 4, 8, 12, 24, 36, 48 weeks) after the surgery. The details of each visit will be mentioned in 6.3. Study Visits and Procedures.

## **5. STUDY DESIGN**

## 5.1. Summary of Study Design

We propose to conduct a randomized controlled trial with three treatment arms: immediate implant, immediate implant combined with SCTG, and immediate implant combined with ADM. Patients (age $\geq$ 18 year-old) need to have single maxillary unrestorable tooth which is planned to be replaced with an implant in the esthetic zone (maxillary premolar to premolar). The unrestorable tooth has adjacent teeth and acceptable periodontal condition (probing depth  $\leq$ 4mm, gingival recession $\leq$  1mm at six sites: mesial-buccal, mid-buccal, distal-buccal, distal-palatal, mid-palatal, distal-palatal). The patients have to be systemically healthy or have controlled common systemic conditions (controlled hypertension, controlled diabetes HbA1c up to 7 %). Smokers having cigarettes  $\leq$  10/per day are eligible but they are encouraged to stop smoking 1 week prior to and up to 2 months after implant placement (Bain, 1996). The primary outcome of the study is the ridge dimensional alterations at six months and 12 months after surgery while the secondary outcomes are the changes of gingival level, gingival thickness, width of keratinized gingiva, alveolar bone level, and bone dimension.

## 6. METHODS AND ASSESSMENTS

### 6.1. Randomization and Blinding

Patient allocation to the three groups (immediate implant combined with SCTG, immediate implant combined with ADM, immediate implant alone) was performed by a blinded non-surgeon following tooth extraction, based on computer-generated randomization (MATLAB). The surgeon will be noticed the randomization results the date of performing surgery. Patients will not be blinded given the patients definitely know the treatments that they receive due to the characteristics of procedures.

### 6.2. Contraception and Pregnancy Testing

Pregnancy status of subjects who are women with childbearing potential will be orally confirmed at the screening. The pregnant subjects will be excluded from the study.

### 6.3. Study Visits and Procedures

#### a. Screening Visits and Procedures

Study protocol and consent forms will be approved by the Institutional Review Board at the University of Texas Health Science Center at Houston. The trial will be registered with ClinicalTrials.gov. The clinicians and dental students in UTSD and PISH will be told the information of this clinical trial. The potential subjects who are interested in participating in this project will be referred to the clinic of Department of Periodontics and Dental Hygiene, UTSD or the clinic of PISH for initial screening. The principal investigator will confirm the eligibility of these patients. All patients will have dental cone-beam computed tomography before the surgery given the implants will

be placed in the highly esthetic zone (Benavides et al. 2012). All patients will sign the consent forms and are informed of the details of study procedures as well as potential complications. After informed consent is obtained, and initial periodontal therapy and oral hygiene instruction, whenever indicated, the surgery will be scheduled as the first visit.

At the first appointment, all clinical measurements will be performed (probing depth (PD), clinical attachment level (CAL), bleeding on probing (BOP), plaque index (PI)) and the impression of maxillary and mandibular dentition will be taken. One periapical radiography of the surgical site will be taken after the surgery is finished. After verification that the local anatomical inclusion criteria are met, patients will be randomized to one of three treatment groups. All implants will be placed according to standard protocol at a subcrestal position (1 mm below the buccal crest) engaging the palatal wall without elevation of a mucoperiosteal flap. The gap between the implant and alveolar bone will be filled with xenograft (Geistlich Bio-Oss®) and covered by collagen dressing (CollaTape®). In the groups having soft tissue augmentation, intrasulcular incisions will be carried out to partially dissect the buccal flap from mesial papilla to distal papilla. The SCTG or ADM will be inserted into the dissected buccal flap. The SCTG will be subepithelially harvested from the palate of the patient. The width of tissue graft will be equal to the distance between the interproximal papillae on the level of buccal gingival margin. The length of SCTG will be standardized as 10 mm. The thickness of SCTG will be standardized as 1-1.5mm. The size of ADM will be standardized following the same principle. The SCTG tissue graft or ADM will be stabilized by sling suture (chromic gut 5-0).

In the three groups, the straight healing abutment will be delivered immediately after implant placement provided that the implant shows primary stability and has engaged in the bone with an insertion torque of 25 Ncm or more (Norton 2004). In case of a lower insertion torque, the protocol will be abandoned, a cover screw will be placed, and a two stage implant protocol will be followed. All patients will receive a permanent restoration at 6 months after surgery, if the implant is deemed to be successful (Misch et al. 2008). The placement of xenografts aims to optimize the esthetic outcomes.

All patients will receive Amoxicillin 500mg, t.i.d, (for penicillin allergic patients: Clindamycin 150 mg, q.i.d) for seven days following surgery. Patients will be instructed to use mouth rinse (Chlorhexidine 0.12%) twice daily during the first two weeks and avoid brushing the surgical area for two weeks. All patients will be seen at two weeks following surgery, remove suture, follow up of healing, and oral hygiene; at 4 weeks (supragingival prophylaxis) ; at 8 weeks (supragingival prophylaxis); at 3 months (prophylaxis and measurements); at 6 months (prophylaxis, measurements, periapical radiography, cone beam computed tomography, impression for the permanent restoration). The permanent restoration will be delivered within one month following the final impression taken. After the crown placement, the patients will be seen at 9 months (prophylaxis) and 12 months (prophylaxis, measurements, periapical radiography, impression).

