## **8.3. Blinding**

The surgeons and patients cannot be blinded because the surgeons will be told which procedure to perform at the first visit and patients will be aware of the procedures that they received after surgery. The patients will be informed of benefits of all the procedures and realize all procedures are supported by scientific evidence.

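### Patients are randomised before insertion torque is known, so a low reading can take a randomised patient off the planned treatment, and nothing keeps the surgeon unaware of the arm during placement

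*Combined protocol and SAP*

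**What the plan says.** - **Eligibility before allocation.** Section 3.3 requires the position of the buccal crest to be "verified after the extraction, before randomization", and gives limits for any fenestration. Torque and primary stability are not listed there.
- **Allocation.** Section 6.3a: "After verification that the local anatomical inclusion criteria are met, patients will be randomized to one of three treatment groups". Implant placement is described in the sentence that follows. Section 6.1 has a blinded non-surgeon allocate after extraction.
- **Torque.** Later in Section 6.3a, the healing abutment is delivered at once if the implant is stable and "has engaged in the bone with an insertion torque of 25 Ncm or more". Otherwise: "In case of a lower insertion torque, the protocol will be abandoned", with a cover screw instead, and a two-stage implant protocol follows.
- **What the surgeon knows.** Section 6.1: "The surgeon will be noticed the randomization results the date of performing surgery". Section 8.3 says surgeons cannot be blinded because "the surgeons will be told which procedure to perform at the first visit".
- **The event is foreseen.** Section 2.4b lists "inability to stabilize the implant due to poor quality of bone" among the study risks, without a rate.
- **Afterwards.** Low torque is not named among the withdrawal reasons in Section 3.5. Section 3.6 allows withdrawn subjects to be replaced, with no enrolment beyond 24 months from its start. Section 11.2c includes data from withdrawn patients in the analysis. No section says how a patient with low torque is followed or analysed.

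**The concern.** The protocol already holds back randomisation until the socket has been inspected, so that patients who fail the anatomical criteria never enter an arm. It does not do the same for torque, the other intra-operative condition that can take a patient off the planned course.

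Two things are at stake. First, patients can depart from planned treatment after randomisation, and if they are then left out or replaced, the comparison is no longer between the groups as randomised. Second, if the surgeon already knows the arm, placement and the reading that triggers the departure are made with that knowledge. Departures, or implant position, could then differ by arm. The primary outcome is change in ridge dimension at the implant site, so comparable placement across arms matters.

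**Working it through.** **1. Order of steps (Sections 3.3, 6.1, 6.3a)**

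| Step, in the order described | Differs by arm? |
|---|---|
| Extraction and anatomical check | No |
| Randomisation | – |
| Flapless placement, 1 mm subcrestal, engaging the palatal wall | No |
| Xenograft in the gap, collagen dressing | No |
| Partial dissection of the buccal flap, SCTG or ADM, suture | Yes |
| Healing abutment, or cover screw if torque is low | No |

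Torque is a property of the seated implant, so it is available after placement, before the first step that differs by arm. Nothing described before the graft requires knowledge of the arm. On the order given, allocation could follow the torque reading.

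**2. How many patients**

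The low-torque rate q is not in the documents, so it is an assumption here. With 42 randomised, the expected number is 42 × q and the chance of at least one is 1 − (1 − q)^42.

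| Assumed q | Expected among 42 | P(at least one) |
|---|---|---|
| 5% | 2.1 | 88% |
| 10% | 4.2 | 99% |
| 15% | 6.3 | >99% |

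**3. The plan's own sample size, and what losses could do to it**

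Inputs from Section 11.1: difference 1 mm, SD 0.9 mm, power 80%, 11 per group, 14 enrolled. For a two-sample t-test, df = 2n − 2 and the noncentrality is (1/0.9) × √(n/2). At n = 11 this is 1.111 × √5.5 = 2.61 with 20 df. One-sided at 0.05, power is 80.8%; at n = 10 it is 77.2%. So 11 is reproduced on a one-sided basis. The plan does not state sidedness. Section 3.1 gives SD 0.85 with the same 11.

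The allowance is 14 − 11 = 3 per arm (3/14 = 21.4%) for all causes, with no share named for low torque.

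The following holds only if every low-torque patient is neither analysed nor replaced, which the plan does not say:

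- Chance that at least one arm loses 4 or more of 14 from this cause alone, 1 − [P(X ≤ 3)]³ with X ~ Bin(14, q): about 1%, 13% and 38% at q = 5%, 10% and 15%.
- Expected loss per arm at q = 10%: 14 × 0.10 = 1.4, leaving 12 to 13.

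| n per arm | One-sided, SD 0.9 | Two-sided, SD 0.9 | Two-sided, SD 0.85 |
|---|---|---|---|
| 14 | 88.8% | 80.8% | 85.0% |
| 13 | 86.6% | 77.6% | 82.1% |
| 12 | 83.9% | 73.9% | 78.6% |
| 11 | 80.8% | 69.8% | 74.7% |

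The bottom row needs 11 in both compared arms. The 1%, 13% and 38% concern any one arm, so the two must not be read together. All three arms losing 3 or more has probability below 0.01%, 0.4% and 4.4% at the same rates.

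**The case against.** The strongest reply is that nobody need be lost. The abandonment sentence directly follows the rule for immediate abutment delivery, so it may cancel only the one-stage abutment. Low torque is not a withdrawal reason, and nothing says that the impressions for the primary outcome stop. Even a withdrawn patient can be replaced, and the data already collected are to be included. This stands against any claim that losses are certain or that the allowance will be used up. It does not remove the point: on the narrow reading there is still a departure after randomisation with no analysis rule, and replacement restores numbers but not the randomised comparison.

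Second, neither Section 6.1 nor Section 8.3 fixes the moment of disclosure. That the surgeon knows the arm during placement is an inference from these sections and the order in 6.3a. This also stands; what can be said is that nothing prevents it.

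Third, room for influence is limited. Depth and wall engagement are prescribed for all implants, torque has a numeric cut-off, and the horizontal and vertical defect dimensions recorded at placement (Section 6.3b, items 2 and 3) would let differences in position be examined by arm. That is fair. It helps to detect a difference afterwards but does not prevent one.

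Finally, the text does not state when the palatal graft is harvested relative to placement, so the shared sequence rests on the order of the narrative.

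**Conclusion.** The point holds as one of design order. Torque becomes known after randomisation, a low value changes what the patient receives, and the arm could be withheld until that reading is made. At assumed rates of 5% to 15%, about 2 to 6 of 42 patients would be affected; the true rate is not given.

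A reader might infer three stronger things that the documents do not support:

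- *That low-torque patients are necessarily lost.* The text allows the reading that only the one-stage abutment step is dropped.
- *That power falls to 75% or 70%.* Those figures assume a two-sided test, 11 left in both compared arms, and no analysis or replacement of the affected patients. On the one-sided basis that reproduces the plan's 11 at SD 0.9, the fall from 14 to 11 is from 89% to 81%, still above target. The power figures are illustrations, not findings.
- *That surgeons would place implants differently by arm.* Nothing suggests this; the design merely leaves it possible.

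The change is cheap and worth making, but the comparison does not fail without it.

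**What to change.** In Sections 6.1 and 6.3a, state that the patient is randomised, and the arm disclosed to the surgeon, only after the implant is seated and the protocol's existing torque criterion is recorded as met, just before the step at which the arms differ. Patients who do not meet it are not randomised and are managed as the protocol already states. Make clear which protocol is abandoned at low torque. In Section 11.2c, add that anyone found ineligible after randomisation is followed and analysed in the assigned arm.

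Cost: the allocation is opened a few minutes later in the same operation, and any arm-specific preparation waits until then. The randomised population is limited to patients with adequate torque, so slightly more may have to consent to reach 42 randomised; at an assumed 10% rate, 42/0.90 = 46.7, about 47 reaching placement. No change to the torque threshold or to clinical handling is proposed.
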